# 5.2. Exclusion Criteria

Participants are excluded from the study if any of the following criteria apply:

NO	EXCLUSION CRITERIA		
Medical Hi	story		
1	History of, or currently active, symptoms or signs suggestive of upper or lower respiratory tract (LRT) infection within 4 weeks prior to the first study visit.		
	
 
a) Any history or evidence of any other clinically significant or currently active systemic comorbidities including psychiatric disorders (includes participants with a history of depression and/or anxiety).
 
b) And/or other major disease that, in the opinion of the Investigator, may put the participant at undue risk, or interfere with a participant completing the study and necessary investigations.
 
The following conditions apply:
 
		
2	
 
Participants with clinically mild atopic eczema/atopic dermatitis and clinically mild psoriasis may be included at the Investigator's discretion (e.g., if small amounts of regular topical steroids are used, no eczema in cubital fossa; moderate to large amounts of daily dermal corticosteroids is an exclusion).
 
Rhinitis (including hay fever) which is clinically active or history of moderate to severe rhinitis, or history of seasonal allergic rhinitis likely to be active at the time of inclusion into the study and/or requiring regular nasal corticosteroids on an at least weekly basis, within 30 days of admission to quarantine will be excluded. Participants with a history of currently inactive rhinitis (within the last 30 days) or mild rhinitis may be included at the PI's discretion.
 
Participants with a physician diagnosed underactive thyroid who have been controlled on treatment for at least 6 months with evidence of a normal thyroid function test can be included at the discretion of the PI.
 
Any concurrent serious illness including history of malignancy that may interfere with the aims of the study or a participant completing the study. Basal cell carcinoma within 5 years of initial diagnosis or with evidence of recurrence is also an exclusion.
 
Participants with a history of resolved mild depression and/or anxiety 3 or more years ago can be included if the Patient Health Questionnaire (PHQ-9) and / or the Generalised Anxiety Disorder Questionnaire (GAD-7) is less than or equal to 4 on admission. Participants with a history of stress related illness, which is not ongoing or requiring current therapy, with good evidence of preceding stressors may be included at the PI's discretion. All participants will be assessed prior to enrolment with a PHQ-9 and GAD-7 questionnaire.
 
Participants with physician diagnosed mild irritable bowel syndrome not requiring reguiring current therapy.
 
		

NO	EXCLUSION CRITERIA
3	Participants who have smoked ≥10 pack years at any time (10 pack years is equivalent to one pack of 20 cigarettes a day for 10 years).
4	A total body weight $\leq$ 50 kg or body mass index (BMI) $\leq$ 18 kg/m  or $\geq$ 35 kg/m  .
5	Females who: a) Are breastfeeding, or b) Have been pregnant within 6 months prior to the study.
6	History of anaphylaxis-and/or a history of severe allergic reaction or significant intolerance to any food or drug, as assessed by the PI.
7	Venous access deemed inadequate for the phlebotomy and cannulation demands of the study.
8	
 
a) Any significant abnormality altering the anatomy of the nose in a substantial way or nasopharynx that may interfere with the aims of the study and in particular any of the nasal assessments or viral challenge, (historical nasal polyps can be included, but large nasal polyps causing current and significant symptoms and/or requiring regular treatments in the last month will be excluded).
 
b) Any clinically significant history of epistaxis (large nosebleeds) within the last 3 months of the first study visit and/or history of being hospitalised due to epistaxis on any previous occasion.
 
c) Any nasal or sinus surgery within 3 months of the first study visit.
 

Prior or Co	a) Evidence of vaccinations within the 4 weeks prior to the planned date of viral challenge, unless medically necessary (e.g., during an outbreak or pandemic
9	
 
situation) and at the PI's discretion.
 
b) Intention to receive any vaccination(s) before the day of Follow-up visit. (NB. No travel restrictions will apply after the Day 28 Follow-up visit).
 
c) Receipt of influenza vaccine in the last 6 months prior to the planned date of viral challenge.
 

10	Receipt of blood or blood products, or loss (including blood donations) of 470 mL or more of blood during the 3 months prior to the planned date of viral challenge or planned during the 3 months after the final visit.
11	
 
a) Receipt of any investigational drug within 3 months prior to the planned date of viral challenge.
 
b) Receipt of three or more investigational drugs within the previous 12 months prior to the planned date of viral challenge.
 
c) Prior inoculation with a virus from the same virus-family as the Challenge virus.
 
d) Prior participation in another HVC study with a respiratory virus in the preceding 3 months, taken from the date of viral challenge in the previous study to the date of expected viral challenge in this study.
 
e) Receipt of a pAb or biologic within the previous 12 months prior to the planned date of viral challenge.
 

NO		
12	
 
a) Confirmed positive test for drugs of abuse and cotinine on first study visit. One repeat test allowed at PI discretion.
 
b) History or presence of alcohol addiction, or excessive use of alcohol (weekly intake in excess of 28 units alcohol; 1 unit being a half glass of beer, a small glass of wine or a measure of spirits), or excessive consumption of xanthine containing substances (e.g., daily intake in excess of 5 cups of caffeinated drinks e.g., coffee, tea, cola).
 
	
13	A forced expiratory volume in 1 second (FEV1) <80%.	
14	Positive HIV, active hepatitis A, B, or C test.	
Other		
15	Those employed or immediate relatives of those employed at hVIVO or the Sponsor.	
16	Any other finding that, in the opinion of the Investigator, deems the participant unsuitable for the study.	

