# 3. Objectives and Endpoints

Objectives	Endpoints	
Primary		
• To evaluate the effect of SAB-176, in reducing influenza viral load quantitative reverse transcriptase-polymerase chain reaction (qRT-PCR) when compared to placebo.	
 
VL-AUC of Influenza A/California/2009 H1N1 virus, as determined by qRT-PCR on nasal samples.
 
	
Secondary		
• To further evaluate the effect of SAB-176, in reducing viral loads / viral shedding in qRT-PCR due to Influenza A/California/2009 H1N1 virus, compared to placebo.	
 
Peak viral load as defined by the maximum viral load determined by quantifiable qRT-PCR measurements.
 
Duration of influenza quantifiable qRT-PCR measurements.
 
	

 
To evaluate the effect of SAB-176, in reducing viral loads / viral shedding in cell culture due to Influenza A/California/2009 H1N1 virus, compared to placebo.
 
	
 
Area under the viral load-time curve (VL-AUC) of Influenza A/California/2009 H1N1 virus, as determined by cell culture measurements.
 
Peak viral load as defined by the maximum viral load determined by quantifiable cell culture measurements.
 
Duration of influenza quantifiable cell culture measurements.
 
	

 
To evaluate the effect of SAB-176, in reducing symptoms due to Influenza A/California/2009 H1N1 virus, compared to placebo.
 
	
 
Area under the curve over time of total clinical symptoms score (TSS-AUC) as measured by graded symptom scoring system (categorical and visual analogue scales).
 
Peak symptom diary card score: peak total clinical symptoms (TSS) as measured by graded symptom scoring system (categorical and visual analogue scales).
 
Peak daily symptom score: Individual maximum daily sum of symptom score.
 
Number (%) of participants with Grade 2 or higher symptoms.
 
	

Objectives	Endpoints	
To evaluate the effect of SAB-176, in reducing the incidence of symptomatic infection due to Influenza A/California/2009 H1N1 virus, compared to placebo.	
 
RT-PCR-confirmed symptomatic influenza infection defined as:         
 
RT-PCR-confirmed influenza infection, AND
 
Clinical symptoms.
 
 
 
Culture lab-confirmed reduction of symptomatic influenza infection defined as:         
 
Lab-confirmed culturable influenza infection, AND
 
 
 
	

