# 6.5. Concomitant Therapy

Any medications taken and changes in medications from the time the participant signing the study specific ICF, up to final study contact Day 28 (±3 days), will be recorded in the source data. Any medication (including over-the-counter or prescription medicines, vitamins, and/or herbal supplements) or other specific categories of interest that the participant is receiving at the time of enrolment or receives during the quarantine/outpatient stage will be stored, prescribed and administered in line with their label-specific requirements, and recorded according to the parameters required by the clinical database.

Participants will be reminded to refrain from using any over-the-counter medication without the approval of the Investigator and must notify the study site as soon as possible if they are prescribed any medication. All medications must be stopped prior to the planned date of viral challenge unless in the opinion of the Investigator and/or Sponsor's Medical Expert (SME), the medication will not interfere with the study procedures or compromise participant safety.

Medications prohibited throughout the study are shown in Table 3.

Prohibited medication	Washout
Systemic (oral and parenteral) antiviral drugs.	4 weeks prior to first study visit.
Influenza vaccine	6 months prior to first study visit.
Use or anticipated use during conduct of the study of concomitant medications (prescription and non- prescription), including vitamins or herbal and dietary supplements within the specified windows, unless in the opinion of the Investigator the medication will not interfere with the study procedures or compromise participant safety.	
 
Within 7 days prior to the planned date of viral challenge:
 
Herbal supplements
 
Any medication or product (prescription or over the counter) for symptoms of nasal congestion
 
Short and long-acting antihistamines.
 
Within 21 days prior to the planned date of viral challenge:
 
Chronically used medications, vitamins, or dietary supplements, including any medication known to be moderate/potent inducers or inhibitors of cytochrome P450 (CYP) enzyme.
 

Any IMP used in another trial	Within 3 months (or 5 half-lives of the IMP used in the other trial), whichever is greater, prior to the planned date of viral challenge.

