#### Table 6: Methods for Analysis of Secondary Endpoints

Endpoints	Planned analysis
Peak viral load of VL-AUC of Influenza A/California/2009 H1N1 virus as defined by the maximum viral load determined by quantifiable qRT-PCR measurements in nasal samples starting two days post viral challenge (Day 2) up to discharge from quarantine.	Wilcoxon-rank-sum test (alternative: t-test if underlying assumptions valid)
Duration of influenza quantifiable qRT-PCR measurements in nasal samples.	Wilcoxon-rank-sum test (alternative: t-test if underlying assumptions valid)
Area under the curve over time of total clinical symptoms score (TSS-AUC) as measured by graded symptom scoring system (categorical and visual analogue scales).	t-test if underlying assumptions valid (alternative: Wilcoxon-rank- sum test)
Peak symptoms diary card score: peak total clinical symptoms score (TSS) as measured by graded symptom scoring system (categorical and visual analogue scales).	t-test if underlying assumptions valid (alternative: Wilcoxon-rank- sum test)
Peak daily symptom score: Individual maximum daily sum of symptom score.	t-test if underlying assumptions valid

Endpoints	Planned analysis
	(alternative: Wilcoxon-rank- sum test)
Number (%) of participants with Grade 2 or higher symptoms.	Chi-square test
Incidence of symptomatic infection due to Influenza A/California/2009 H1N1 virus, compared to placebo as measured by: RT-PCR-confirmed symptomatic influenza infection defined as:	Chi-square test (on the composite and each component)

RT-PCR-confirmed influenza infection, AND

Clinical symptoms

	

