#### Assessment

#### Challenge Virus Symptoms

The Investigator will assess, and review Challenge virus related symptoms recorded in participants' hVIVO symptom diary cards. Symptoms greater than Grade 0 will be expected and presumed to represent virus infection consequent to Viral Challenge and will not be additionally captured as AEs unless they meet the definition of an AE and are deemed to be clinically significant (in the opinion of the Investigator) to be classed as AEs.

Following Viral Challenge all unexpected (in the opinion of the Investigator) symptoms post inoculation will be captured as AEs, along with all other occurrences that meet the criteria for an AE.

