# 10.6.2. Study definition of infection and illness

TERM	CRITERIA (RESPIRATORY SYNCYTIAL VIRUS, HEART RATE VARIABILITY AND INFLUENZA STUDIES)			
Seroconversion	A ≥4-fold increase in Virus specific antibodies from baseline to follow-up post-quarantine			
The following definitions should only be applied to data collected from Day 1 onwards				

TERM	CRITERIA (RESPIRATORY SYNCYTIAL VIRUS, HEART RATE VARIABILITY AND INFLUENZA STUDIES)
Lower Respiratory Tract Illness	
 
Any one of the following signs and/or symptoms on two consecutive scheduled assessments, at least one of which must feature Grade 2 severity, or if any of the following attain Grade 3 severity once: 
 
Self-reported symptoms: cough, shortness of breath, chest tightness and wheeze.
 
Physician findings: Abnormal breath sounds externally (e.g., stridor, wheezing) and on chest auscultation (rhonchi, crepitations or other).
 

Upper Respiratory Tract Illness	
 
Any one of the following signs and/or symptoms on two consecutive scheduled assessments, at least one of which must feature Grade 2 severity, or if any of the following attain Grade 3 severity once: 
 
Self-reported symptoms: rhinorrhoea (runny nose), nasal congestion (stuffy nose), sore throat, sneezing.
 
Physician findings: nasal discharge, otitis, pharyngitis, sinus tenderness.
 
 
 

Systemic Illness	Fulfils the criteria for febrile illness, or fulfils the definition of upper respiratory tract illness and/or lower respiratory tract illness and any one of the following symptoms on two consecutive scheduled assessments, at least one of which must feature Grade 2 severity, or if any of the following attain Grade 3 severity once: • malaise • headache • muscles and/or joint ache • chilliness • feverishness.
Febrile Illness	Any occurrence of temperature $\geq$ 37.9°C (confirmed by a repeat measurement as $\geq$ 37.9°C within 20 to 60 minutes).

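### Exclusion 2 leaves it unclear whether active mild rhinitis, or past moderate to severe rhinitis now quiet, bars entry, and the symptom scores are analysed without the pre-challenge diary score already collected

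*Combined protocol and SAP*

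**What the plan says.** **Eligibility.** The rhinitis condition in section 5.2, exclusion 2, has two sentences. The first excludes "Rhinitis (including hay fever) which is clinically active or history of moderate to severe rhinitis". It also excludes a seasonal allergic history expected to be active around entry, and at least weekly use of nasal steroids, and it ends with a window of 30 days before admission. The second reads: "Participants with a history of currently inactive rhinitis (within the last 30 days) or mild rhinitis may be included at the PI's discretion". Section 5 permits no waivers.

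**Medication.** Table 3 in section 6.5 lists "Short and long-acting antihistamines" and nasal congestion products under a 7-day washout before challenge, unless the Investigator judges that the medication will not interfere.

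**Diary and endpoints.** Section 8.11 grades 13 items, including runny nose, stuffy nose and sneezing. Table 6 gives a t-test or Wilcoxon test for TSS-AUC, peak TSS and peak daily score, and a chi-square test for "Number (%) of participants with Grade 2 or higher symptoms". None of these four carries an infection condition. Symptomatic infection does: section 3 defines it as "RT-PCR-confirmed influenza infection, AND" clinical symptoms, with no threshold for the symptoms. Among the self-reported symptoms for upper respiratory illness, section 10.6.2 lists "rhinorrhoea (runny nose), nasal congestion (stuffy nose), sore throat, sneezing", with a Grade 2 or Grade 3 requirement.

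**Attribution and baseline.** For adverse event handling, section 10.3.6.2 states: "Symptoms greater than Grade 0 will be expected and presumed to represent virus infection consequent to Viral Challenge". The default baseline in section 8 is the nearest value before dosing. Dosing is on Day 1, after challenge. The Schedule of Activities also places a diary assessment on Day 0 before challenge.

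**The concern.** Two screening physicians could read exclusion 2 differently for the same volunteer, and the waiver rule means that one of them would be recording an eligibility deviation.

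Nasal symptoms already present at entry are scored on the same diary items as influenza symptoms. SAB-176 would not be expected to reduce allergic symptoms, so they inflate variance and pull the arms together on the secondary symptom endpoints. The protocol collects a pre-challenge score that could absorb part of this noise, but Table 6 does not use it. With 30 participants per arm, the secondary comparisons have little precision to spare.

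**Working it through.** **1. The plan's own sample size.** Inputs from section 9.2: 60% reduction, 81% coefficient of variation, 80% power, two-sided 5%. With the control mean set to 1 and equal SDs:

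n per arm = 2 × (1.960 + 0.842)² × (0.81/0.60)² = 2 × 7.85 × 1.8225 = 28.6, so 29.

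The t-test version gives 29.6, so 30 per arm and 60 in total, with power 0.805. The stated figure reproduces. It concerns qRT-PCR viral load, and no symptom score enters it.

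**2. The two eligibility sentences side by side.**

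| Volunteer | First sentence | Second sentence |
|---|---|---|
| Mild rhinitis, active now | Excluded as clinically active | Includable as mild, unless the phrase about history also governs mild |
| Past moderate to severe, inactive for 30 days | Excluded, unless the 30-day window governs the whole list | Includable as inactive; no severity limit |
| Seasonal allergy expected to be active at entry | Excluded by its own clause | Includable only if read as mild |

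Each conflict disappears on one reading and remains on another, and the text does not choose. If history governs both terms, the mild limb adds only people whose mild rhinitis was not quiet over the 30 days. That is close to the group the first sentence targets.

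**3. Share of the score.** Eleven items have a maximum of 3 and two have a maximum of 4: 11 × 3 + 2 × 4 = 41. The three nasal items carry 3 × 3 = 9, and 9/41 = 22%. On the visual analogue card they are 3 of 13 items, or 23%. Steady Grade 1 on all three adds 3 points at each assessment, or 3 × 7 = 21 score-days from Day 1 to Day 8. The documents give no expected TSS-AUC, so this cannot be turned into a share of an effect.

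**4. Symptomatic infection: an illustration.** The 65% infection rate comes from Table 1 and is applied to both arms. Three inputs are assumptions:
- the proportion s of infected placebo participants with true symptoms is 50% to 80%;
- the proportion r of entrants with current rhinitis, always counted as clinical symptoms, is 5% to 20%;
- true symptoms given infection fall by 60% on SAB-176.

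Placebo rate = 0.65 × [s + (1 − s)r]. Active rate = 0.65 × [0.4s + (1 − 0.4s)r]. The difference is 0.65 × 0.6s × (1 − r), so the absolute effect shrinks by the fraction r.

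For s = 0.65 and r = 0.10, placebo moves from 0.4225 to 0.4453 and active from 0.1690 to 0.2171. The difference falls from 0.2535 to 0.2282.

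| s | r | Extra per 30, placebo | Extra per 30, active | Power without | Power with |
|---|---|---|---|---|---|
| 0.50 | 0.05 | 0.49 | 0.78 | 0.435 | 0.379 |
| 0.50 | 0.20 | 1.95 | 3.12 | 0.435 | 0.253 |
| 0.65 | 0.10 | 0.68 | 1.44 | 0.579 | 0.466 |
| 0.80 | 0.05 | 0.19 | 0.66 | 0.720 | 0.666 |
| 0.80 | 0.20 | 0.78 | 2.65 | 0.720 | 0.499 |

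**5. What the covariate buys.** With correlation ρ between the pre-challenge score and the outcome, ANCOVA reduces residual variance by about the factor 1 − ρ². The documents do not give ρ. If all 60 are analysed, residual degrees of freedom go from 60 − 2 = 58 to 60 − 3 = 57.

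**The case against.** The case for leaving the plan alone is substantial.

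- **No definite contradiction.** A reader might infer that the two sentences flatly conflict. They can be read consistently, and the clause on seasonal rhinitis catches the obvious hay-fever case. This stands: the text is ambiguous, not self-refuting.
- **Other filters exist.** Exclusion 1 covers "currently active, symptoms or signs suggestive of upper or lower respiratory tract (LRT) infection within 4 weeks prior to the first study visit". Allergy history is taken at screening and on Day -2/-1, and there is a directed nasal examination before challenge. These reduce the number who enter, but exclusion 1 concerns infection rather than allergy, and none of them settles the wording.
- **Rhinitis cannot make an influenza case.** A reader might infer that rhinitis sufferers would be scored as having symptomatic influenza. The composite also requires laboratory confirmation, and upper respiratory illness requires two consecutive assessments with at least one at Grade 2, or Grade 3 once. This stands. Clinically mild rhinitis could still score Grade 2, since that diary grade covers bothersome symptoms that do not disrupt activities.
- **Untreated entry is not established.** The Table 3 washout has an Investigator exception.
- **An uneven split is conjecture.** Three affected participants against none would move the Grade 2 or higher rate by at most 3/30 = 10 percentage points, but nothing in the documents supports that split. Some of the three could reach Grade 2 from influenza anyway.
- **The primary result.** A reader might infer that membership of the Per Protocol set would turn on this wording. Section 9.3 removes only major deviations likely to affect the efficacy evaluation, and section 9.4.3.2 has them reviewed blind. The documents do not show that rhinitis would qualify.
- **The SAP may already adjust.** Section 9.4.2.2 allows analysis of covariance and defers detail to the SAP. I found no separate SAP text in the document, so this stays open. Table 6 as written names only unadjusted tests.

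**Conclusion.** The concern holds in limited form. Exclusion 2 is ambiguous for two kinds of volunteer. Background nasal symptoms that enter add noise to TSS-AUC, peak TSS, peak daily score and the Grade 2 or higher count, through items worth 22% of the categorical scale. In an infected participant they can supply the symptom half of symptomatic infection.

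Under the assumptions shown, power for that composite falls from 0.44–0.72 to 0.25–0.67. This is an illustration, and a pessimistic one, because every rhinitis entrant is counted as symptomatic. The documents do not say how many would enter, so the true loss could be negligible.

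The primary endpoint and the sample size of 60 are untouched, and section 9.1 rests the efficacy conclusion on the primary analysis alone. With blinded 1:1 randomisation, the expected effect is dilution towards no difference. The documents do not support reading it as bias favouring either arm.

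**What to change.** 1. **Section 5.2, exclusion 2.** Reconcile the two sentences so that the status of currently active mild rhinitis, and of past moderate to severe rhinitis now inactive, is explicit. Which way each is settled is a clinical decision for the sponsor and investigator. Cost: a wording amendment.

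2. **Table 6 and the SAP.** Analyse TSS-AUC, peak TSS and peak daily score by ANCOVA with treatment and the Day 0 pre-challenge diary score as covariate, using the matching scale for the categorical and visual analogue versions. Use a rank-based ANCOVA if normality fails. This replaces the unadjusted t-test or Wilcoxon test. Name the Day 0 pre-challenge assessment explicitly, because the default pre-dosing baseline would fall after challenge. Cost: one degree of freedom and a line of text; the data are already scheduled. The gain is small if most pre-challenge scores are zero.

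3. **Binary endpoints.** Leave the Grade 2 or higher and upper respiratory illness definitions unchanged. A count restricted to grades above the participant's own pre-challenge grade may be added as a sensitivity analysis only. As a main definition it would change the endpoint and could discard true influenza symptoms of the same grade. The covariate does not help these endpoints or symptomatic infection; for them the control is clear eligibility wording.
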